# 4.2. Primary Outcomes

- To assess the circulating levels of adiponectin, leptin, tumour necrosis factor alpha (TNFα), interleukin 6 (IL-6), Insulin like growth factors 1 and 2 (IGF 1 and 2) in blood and at tissue level (endometrial tissue, adipose tissue, lymph node) from women with endometrial cancer (study population) and in the blood +/- endometrial tissue (control population) and to compare the results between the two groups.
- Additional tests on the samples collected looking at the cancer tissue
  microenvironment for infiltrating inflammatory cells +/- their secretions or other
  adipocytokines. We may also look at the tumour microbiome to look for any
  commensal bacteria or micro-organism and if available, to compare with tissue
  micro-environment and microbiome of normal endometrial tissue from control
  population.
- 3. To determine whether there is a correlation between these markers and obesity (classified by WHO category of BMI) after adjusting for confounding factors like age, parity, menopause, use of HRT/ hormonal contraception, smoking, diabetes and hypertension.

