### 5. STUDY DESIGN and METHODS of DATA COLLECTION AND DATA ANALYSIS

# 5.1. Study design

All patients being referred to the Royal Surrey NHS Foundation Trust with diagnosed uterine cancer will be given the research information leaflet and invited to participate as the study

population of the research. Female patients being referred to Royal Surrey NHS foundation Trust for benign conditions (specifically not endometrial cancer) will be invited to participate as the control population.

Initially, an invitation letter will be sent alongside the patients' clinic appointment letter to inform them of the study and give them time for preliminary consideration of the study. Patients will then be approached in the outpatients' clinics after the initial consultation by the clinician. Alternatively, patients may be approached over phone and information about the study given at that time. The call will be scheduled after the clinic appointment visit so that the patient will have received the Invitation Letter that is sent out with the initial Appointment Letter, allowing patients sufficient time to consider the study. Patients will be given a participant information leaflet detailing the study rationale, methodology and analysis in clinic or alternatively the leaflet will be sent by post/ email (in case of telephone consultations). Patients who agree to participate in the study will be asked to sign a consent form after explanation at a later appointment.

Demographic data will be collected at the same time to correlate various risk factors associated with the development of uterine cancer. The data collected will include age, parity, smoking status, menopausal status, medications used, use of Hormone Replacement Therapy (HRT)/ hormonal contraception, and prevalence of diabetes and hypertension. This data will be collected by:

- Taking a medical history from the patient in clinic
- Patients' medical notes

This data will be directly entered into an existing departmental database for Gynaecological oncology which is password protected and stored on NHS computers.

Study participants will then have 30mls (2 ½ tablespoons) of venous blood taken on the day of the surgery and control participants will also have 30mls of venous blood collection alongside their clinic appointment.

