#### 6. STUDY SETTING

Study patients will be recruited when attending a clinic in the department of Gynaecological Oncology at Royal Surrey NHS Foundation Trust. Private consultation rooms are available here for discussing the study, history taking and consenting.

Blood sample will be collected on the day of the surgery when they are in the theatres and then repeated on day 1 post-operative in gynaecology ward and at 3 or 6 months post-surgery follow-up in clinic.

Tissue samples will be obtained from the following areas:

- 1. Adipose tissue from the main theatres at Royal Surrey NHS Foundation Trust
- 2. Uterine cancer tissue and lymph node from the histopathology department after they have finished analysis.

For those women recruited undergoing chemotherapy, blood sample will be procured at initial consultation and after 3rd (with the blood test before the fourth cycle of chemotherapy) and 6th cycles of chemotherapy. This can be performed in the Department of Gynaecological Oncology at Royal Surrey NHS Foundation Trust.

All samples (blood and tissue) will then be transferred to the Leggett Building at University of Surrey for processing and storage following HTA regulations. The samples will be double boxed for transfer. The outside box will be an icebox. The PI will personally transport the tissues by foot from the hospital to the Leggett building as they are very near geographically and it is a short 4 minutes' walk.

Control patients will be recruited when they attend a clinic appointment at Royal Surrey NHS Foundation Trust for any benign condition. Blood sample will be collected during their clinic appointment after written consent. If they are having any uterine surgery, endometrial tissue will be collected after histopathological diagnosis from the histo-pathology department.

Samples will also be stored anonymised (in case of patients who give consent) in Leggett building, University of Surrey following all regulations by HTA) for use in ethics approved future research project.

Historical samples / tissue blocks stored in the oncology department in the Leggett building, University of Surrey, from a previous study will also be used if appropriate consent is in place.

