### 7.1. Inclusion criteria

- 1. Study population- Women diagnosed with endometrial cancer
- 2. Control population Women being seen in clinic for benign conditions
- 3. Age 18 or above
- 4. Of sound mind so they can give informed consent
- 5. Historical tissue sample/ blocks from previous cases in the oncology department in the Leggett building also be used if appropriate consent is in place.

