#### 7.2. Exclusion criteria

- 1. Under 18yrs age
- 2. Unable to give consent /denies consent

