# 7.4.1. Sample identification

Patients diagnosed with endometrial cancer will be identified through the Gynaecological Oncology Multi-Disciplinary Team meeting or by the Gynaecological Oncology or Medical Oncology teams. Control population will be identified through the above route or from referral letters to Royal Surrey NHS Foundation Trust.

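### Controls may have any benign condition and no planned analysis uses marker-altering states, so the primary case-control comparison is exposed to bias if those states differ in frequency between groups

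*Combined protocol and SAP*

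**What the plan says.** **Who can be a control.** Section 7.1 gives the criterion as "Control population Women being seen in clinic for benign conditions". Section 6 widens it: "Control patients will be recruited when they attend a clinic appointment at Royal Surrey NHS Foundation Trust for any benign condition". Section 5.1 adds one limit on the condition: women referred "for benign conditions (specifically not endometrial cancer) will be invited to participate as the control population". On finding them, section 7.4.1 says: "Control population will be identified through the above route or from referral letters to Royal Surrey NHS Foundation Trust". The route it refers to is the gynaecological oncology multidisciplinary meeting and the gynaecological and medical oncology teams.

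**Who is excluded.** Section 7.2 has two entries for both groups: "Under 18yrs age" and "Unable to give consent /denies consent".

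**What is recorded.** Besides age and parity, section 5.1 lists "smoking status, menopausal status, medications used, use of Hormone Replacement Therapy (HRT)/ hormonal contraception, and prevalence of diabetes and hypertension". The surgical flow chart in section 5.2 adds medical history and concomitant medication. The benign diagnosis of a control is not among the listed items.

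**What is analysed.** The first primary outcome in section 4.2 compares six markers (adiponectin, leptin, TNF-alpha, IL-6, IGF-1, IGF-2) between cases and controls. The third, on markers and obesity, is to be assessed "after adjusting for confounding factors like age, parity, menopause, use of HRT/ hormonal contraception, smoking, diabetes and hypertension". Section 5.5 adjusts its Cox model for age, stage, grade and histology. For the case-control comparison it says only that results will be compared, and names no model or covariates.

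**The concern.** A control's reason for attending can itself act on the outcome being measured. The Background states that macrophages in an inflammatory environment secrete TNF-alpha and IL-6, and both are study markers. A woman attending for an infective or inflammatory benign condition satisfies sections 7.1 and 7.2 as written, as does a woman on steroid or anti-cytokine treatment. Cases are selected through one disease and controls through an open set of conditions, so there is no design reason to expect such states to be equally common in both groups.

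If they are more common in controls and raise a marker, a true excess in cases is partly hidden. If there is no true difference, a spurious one can appear. The study summary aims at prognostic or diagnostic biomarkers, so the control group has to be interpretable.

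**Working it through.** The plan gives no power, effect size or SD, so there is no figure of its own to reproduce. The check has two parts.

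**1. Does any part of the plan prevent the imbalance?**

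| Possible safeguard | Section | Finding |
|---|---|---|
| Exclusion | 7.2 | Age and consent only |
| Restriction of control condition | 5.1, 6, 7.1 | Benign, not endometrial cancer; nothing further |
| Eligibility check | 5.2, 5.3 | Listed, but no restriction is defined beyond 7.1 and 7.2 |
| Matching | none | Not planned |
| Adjustment, case-control | 5.5 | No covariates named |
| Adjustment, marker-obesity | 4.2 | Belongs to another analysis; does not name infection, inflammatory disease, pregnancy or immunomodulating drugs |
| Data that could be used | 5.1, 5.2 | Medications and history recorded; no analysis uses them |

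None does.

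**2. How large could the effect be?**

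From section 7.3: 30-60 cases, with as many controls as cases. From section 5.5: significance at P<0.05, taken here as two-sided. Assumed, because the documents give no values: a share f_controls of controls and f_cases of cases has a marker shifted upward by s SD, and the true case excess is 0.50 SD.

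Bias in the control-minus-case direction = (f_controls - f_cases) x s.

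Power (normal approximation) = Phi(d / sqrt(2/n) - 1.96), where d is the difference that remains. For n = 60 per group, sqrt(2/60) = 0.1826.

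- No bias: 0.50 / 0.1826 = 2.739, power 0.78.
- f_controls = 15%, f_cases = 0, s = 1: bias 0.15, d = 0.35; 0.35 / 0.1826 = 1.917, power 0.48. Allowing for the extra spread in controls (variance 1 + 0.15 x 0.85 = 1.1275) gives 0.46.
- f_controls = 15%, f_cases = 5%, s = 1: bias 0.10, d = 0.40, power 0.59.
- f_controls = f_cases: bias 0, d = 0.50.

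False-positive rate when there is no true difference, no case is affected and s = 1 (nominal 5%):

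| f_controls | 60 per group, normal approximation | 60 per group, Mann-Whitney simulation | 30 per group, normal approximation |
|---|---|---|---|
| 10% | 8.3% | 7.8% | 6.7% |
| 20% | 18.4% | 16.8% | 11.6% |
| 30% | 34.6% | 32.5% | 19.7% |

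With 20% affected in both groups, the simulated rate stays near 5% (5.2% for s = 1 and 4.6% for s = 2, at 60 per group). The effect depends entirely on a difference between the groups. For scale, 60 per group detects 0.51 SD with 80% power.

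**The case against.** - **The pool is probably narrower than the wording.** A reader might infer that controls can come from any clinic in the hospital. The text says a clinic appointment at the Trust. Section 7.4.1 names the gynaecological oncology route first, section 7.4.2 has that team take consent, and some controls are expected to have uterine surgery. A mainly gynaecological pool is likely. This stands, although no sentence requires it, and gynaecological conditions can also be inflammatory.
- **Cases are equally unrestricted.** A reader might take the bias to be f x s for the control share alone. That is right only if no case is affected. Shifts in opposite directions would also partly cancel. Both points stand, and the power loss is shown as a worst case for that reason.
- **The adjustment list is for another question.** A reader might conclude that the stated covariates fail to remove the bias. The list in section 4.2 belongs to the marker-obesity analysis and is open-ended. The accurate statement is that no covariates are given for the case-control comparison.
- **Most of the data already exist.** Medications and history are collected, and referral letters or notes should show the benign diagnosis. This stands, and it makes the remedy cheap. It does not commit anyone to using the data.
- **Inflamed benign controls are relevant to a diagnostic marker.** Removing all of them would give unusually healthy controls and could exaggerate discrimination. Archived cases also cannot be screened at the draw. Both points stand and argue against broad new exclusions.
- **Drug and pregnancy effects are not in the documents.** True. Only the link from inflammation to TNF-alpha and IL-6 is.

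**Conclusion.** The point holds as a gap in control definition, data capture and analysis. Nothing in eligibility, matching or the planned analysis prevents marker-altering states from differing between controls and cases, or would reveal that they did.

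The documents do not show that a bias exists or which way it runs. They give no frequency of these states in either group and no size of shift. The fall in power from 0.78 to 0.48 is the largest loss under f_controls = 15% and s = 1 SD, since it sets the case share to zero, and it uses the top of the recruitment range. It is not a forecast, and with equal shares the bias is zero. The claim that pregnant or drug-treated controls would create or reverse a difference goes beyond what the documents support.

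The study is exploratory, so this does not invalidate it. It does affect how the first primary outcome can be read, and it is worth correcting while the data can still be captured.

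**What to change.** 1. **Section 5.1.** Add the control's benign diagnosis as a data item. For both groups, record at the baseline draw: pregnancy or recent delivery, active infection, active inflammatory disease, and current corticosteroid, anti-cytokine or immunosuppressive treatment. For archived cases, take these from the notes where available.
2. **Section 5.5.** Prespecify that the primary case-control comparison is repeated without women who have any of these states, by the same rule in both groups. Report the mix of control diagnoses and the number of women affected in each group.
3. **Section 7.2, optional.** State that women who are pregnant or have an active acute infection at the draw are not enrolled prospectively.

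Do not exclude all inflammatory benign disease: those women are relevant comparators for the diagnostic aim.

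The cost is an amendment, a few proforma fields and one sensitivity analysis in a somewhat smaller sample. Data for archived cases will be incomplete, so the rule cannot be applied as fully to them; the report should say for how many the states are unknown. Items 1 and 2 turn no one away. Item 3 would slow recruitment slightly.

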#### 7. SAMPLE AND RECRUITMENT

Potential participants will be identified in the Royal Surrey NHS Foundation Trust – either seen here or referred here and receiving her treatment here.

### 7.1. Inclusion criteria

- 1. Study population- Women diagnosed with endometrial cancer
- 2. Control population Women being seen in clinic for benign conditions
- 3. Age 18 or above
- 4. Of sound mind so they can give informed consent
- 5. Historical tissue sample/ blocks from previous cases in the oncology department in the Leggett building also be used if appropriate consent is in place.

#### 7.2. Exclusion criteria

- 1. Under 18yrs age
- 2. Unable to give consent /denies consent

# 7.3. Sample size

We will aim to recruit 30-60 patients with diagnosed endometrial cancer in the study. This sample size will also include archived tissue sample (formerly consented and stored in Leggett building for use in future ethical research). We will aim to recruit as many patients in the control population as in the study population, aiming for a total (study + control population) of 100-120 patients.

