# **STUDY SUMMARY**

STUDY TITLE	Adipocytokines and their relationship with		
	obesity and endometrial cancer		
SHORT TITLE	Adipocytokines in endometrial cancer		
STUDY DESIGN	exploratory biomarker study		
STUDY PARTICIPANTS	Study population - patients presenting to		
	Royal Surrey NHS Foundation Trust with		
	endometrial cancer, identified at the MDT		
	Control population - female patients		
	without endometrial cancer, referred for		
	benign condition.		
PLANNED SIZE OF SAMPLE	100-120		
FOLLOW UP DURATION	N/A		
PLANNED STUDY PERIOD	36-48 months		
RESEARCH QUESTION /AIM(S)	To investigate the relationship between		
	adipocytokine level in blood and tissue		
	(endometrial cancer tissue, adipose tissue		
	and lymph node) in patients with		
	endometrial cancer and co-relate with BMI		
	to identify peripheral biomarkers that can		
	be used as prognostic or diagnostic tools		

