#### 7.4. Recruitment

All patients seen or referred with endometrial cancer at the Royal Surrey oncology Department will be invited to participate in the study as a part of study population. We will aim to get as many control population from the women referred to Royal Surrey NHS Foundation Trust with benign conditions.

Patients will not receive any payments for participation in the study. We aim to obtain all information and samples at the time of routine visits.

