# 12. PROTOCOL HISTORY

Amendment No.	Protocol version no.	Date issued	Author(s) of changes	Details of changes made
1	0.9	28/06/2021	[name] (PI)	Provision for telephone consultation added
2.	1.0	16/09/2021	[name] (PI)	
 
Control population added.
 
Provision for performing other relevant tests from the samples collected.
 

3.	1.1	27/04/2022	[name] (PI)	
 
Increase in number of control population recruitment.
 
Extension of study duration to 36-48 months.
 

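### The lower case target of 30 does not fit the other two sample-size targets: equal groups with a total of 100-120 require 50-60 cases

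*Combined protocol and SAP*

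**What the plan says.** Section 7.3 (Sample size) sets three targets.

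- **Cases:** "We will aim to recruit 30-60 patients with diagnosed endometrial cancer in the study". Archived material counts towards this figure: "This sample size will also include archived tissue sample".
- **Controls relative to cases, and the total:** "as many patients in the control population as in the study population, aiming for a total (study + control population) of 100-120 patients".

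The study summary gives the same total: "PLANNED SIZE OF SAMPLE 100-120".

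Two other places touch on control numbers. Section 7.4 (Recruitment) says "We will aim to get as many control population from the women referred to Royal Surrey NHS Foundation Trust with benign conditions", with no figure. The third entry in section 12 (Protocol history) records "Increase in number of control population recruitment", also with no figure. Section 7.3 gives no power calculation, effect size or standard deviation, and no rule for what happens if fewer than 50 cases are obtained.

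**The concern.** Three quantities are specified (cases, controls relative to cases, and total), and any two of them fix the third. A case range that starts at 30 with equal groups implies a total that starts at 60, whereas the plan states 100.

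The comparison of markers between cases and controls is part of the first primary outcome in section 4.2, and section 7.3 is the only place that states group sizes. If accrual, archived samples included, ends below 50 cases, the team must depart from either the equal-numbers aim or the stated total. At 30 cases the first choice gives 70-90 controls and the second gives 30. A reader cannot tell from the plan which is intended.

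**Working it through.** **Inputs**

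- Cases, C: 30 to 60, archived samples included (section 7.3).
- Controls, K: equal to C on the plain reading of section 7.3.
- Total, N = C + K: 100 to 120 (section 7.3 and study summary).

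**Step 1. Reproduce the stated total.** With K = C, N = 2C.

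- Upper end: 2 × 60 = 120. This agrees with the plan.
- Lower end: 2 × 30 = 60. The plan says 100, so the shortfall is 100 − 60 = 40.

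**Step 2. Find where all three targets hold.** Solving 100 ≤ 2C ≤ 120 gives 50 ≤ C ≤ 60, so 50-60 cases and 50-60 controls.

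**Step 3. See what each target implies for fewer cases.** Keeping the total requires K between 100 − C and 120 − C.

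| Cases | Total with equal groups | Shortfall from 100 | Controls needed for a total of 100-120 | Controls per case |
|---|---|---|---|---|
| 30 | 60 | 40 | 70-90 | 2.33-3.00 |
| 40 | 80 | 20 | 60-80 | 1.50-2.00 |
| 49 | 98 | 2 | 51-71 | 1.04-1.45 |
| 50 | 100 | 0 | 50-70 | 1.00-1.40 |
| 60 | 120 | 0 | 40-60 | 0.67-1.00 |

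**Step 4. Check whether other text closes the gap.** Archived samples are already inside the 30-60, and section 5.1 describes them as coming from uterine cancer patients, so they add no controls. Sections 7.4 and 12 give no control number.

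**Step 5. Illustrate the effect on precision.** The documents give no effect size, standard deviation or power, so the following is assumed: a two-sample t-test on one unadjusted marker, two-sided 0.05, 80% power. The detectable standardised difference d is the value at which a noncentral t with C + K − 2 degrees of freedom and noncentrality d / √(1/C + 1/K) gives 80% power.

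| Cases + controls | Detectable difference (SD) |
|---|---|
| 30 + 30 | 0.74 |
| 30 + 70 | 0.62 |
| 30 + 90 | 0.60 |
| 40 + 40 | 0.63 |
| 50 + 50 | 0.57 |
| 60 + 60 | 0.52 |

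The marked loss of precision arises only if equal groups are kept with about 30 cases.

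**The case against.** The strongest reply is that these are recruitment aims, and that they can be met together at 50-60 per group. Section 7.4 invites every eligible cancer patient, and nothing stops enrolment at 30 cases or caps the controls, so the choice arises only if accrual ends below 50. That is true, and it limits the practical effect. It does not make the lower bound of 30 consistent with the total.

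A second reply is that the equal-numbers phrase may have meant at least as many controls as cases. The wording in section 7.4 has no comparator and could mean as many as possible, and the protocol history records an increase in control recruitment. On that reading, 30-49 cases with 51-90 controls would reach 100-120. Section 7.3 does not say this, however, and no control number or ratio supports it. If it was the intention, it needs stating.

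Three limits stand:

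- At 49 cases the shortfall is 2 patients, which is negligible for an aim.
- The detectable differences rest wholly on assumptions, and section 5.5 names Mann–Whitney, odds ratios and Cox models but no t-test. They also do not carry over to the tissue comparison, because controls provide endometrial tissue only if they have uterine surgery.
- Reconciling the figures would not by itself tell the reader what precision to expect, since no effect size or power is given. It would settle only the intended group sizes.

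**Conclusion.** The concern holds. On the plain reading of section 7.3, 30-60 cases with equal groups give a total of 60-120, not 100-120. The gap at the lower end is 40 patients, falling to 20 at 40 cases and 2 at 49, and there is none from 50 to 60. The conclusion rests on reading the control aim as one control per case; the illustrative detectable differences play no part in it. As the study is labelled exploratory and no power claim depends on the total, this is an inconsistency that should be corrected rather than a flaw that undermines the design.

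**What to change.** Restate section 7.3 in one of three ways, and align section 7.4 with it:

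1. 50-60 cases and 50-60 controls, total 100-120.
2. 30-60 cases and 30-60 controls, total 60-120. The study summary then changes too.
3. If more than one control per case was intended, remove the equal-numbers aim and state the control number separately, or say that controls are recruited until the total reaches 100-120. With 30 cases that means 70-90 controls; with 60 cases it means 40-60.

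Option 1 raises the minimum case target by 20 (from 30 to 50) at a single centre, and the documents give no accrual rate by which to judge whether that is feasible. Option 2 lowers the minimum total that the plan promises. Option 3 may mean recruiting more controls than cases, each giving 30 ml of blood. Options 2 and 3 need no more cases than now stated. The drafting is a few lines, but section 8.3 requires sponsor advice and, where applicable, REC/HRA submission and approval before a protocol change takes effect.
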